We will explore the effects of the intervention on patient subgroups defined by factors known or hypothesized to have associations with poorer TBI outcome: facility vs. community discharge, race/ethnicity (White, non-Hispanic Black, Hispanic, Other), age (as continuous), male vs. female, lack of or lower degree of caregiver involvement (yes or no), severity of TBI (moderate vs. severe), presence of pre-injury psychosocial limitations (e.g., unemployment, substance abuse, categorized in yes or no) and medical or psychiatric comorbidity (yes or no), as well as study site, resource variability and insurance type (private insurance vs. Medicaid vs. Medicare). These factors will be entered in a single linear regression model in addition to the intervention group, using PART-O-17 as the response variable. Interactions between each factor and the intervention group will be entered in the model and test of interaction will be the test of heterogeneity. Before constructing the model, we will assess whether the explanatory variables (factors) are correlated to each other.

When two or more variables are deemed highly correlated, to avoid problems with collinearity, we will construct the model with the variable that provides the best model (from fit and diagnostic tests).

From previous research, we hypothesize that severity of TBI and presence of pre-injury psychosocial limitations will interact with the intervention group. With our expected sample size, we anticipate being able to address these questions. Some of the factors might not have a statistically significant effect, but have the effect in the expected direction. Effect sizes and confidence intervals will be calculated to express the potential effect of those factors. The results of these analyses will be valuable in designing future studies.

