When missing values are present we will check the missing mechanism, and if it allows for imputation, we will do so according to the appropriate methods for a continuous variable, using multiple imputation strategies (most likely using maximum likelihood methods). We will perform sensitivity analysis of the results by performing the data analysis using the most conservative approach of removing the data from individuals with missing outcome values from the analysis, or if it a missing value in a covariate, removing the covariate from the model. The results of the analysis with imputed data and complete data will be compared to assess whether they differ and both results will be reported. The analyses for aims related to longitudinal trajectory rely on statistical methods (mixed generalized linear models) that are robust to missing data at individual time points. In addition, all reasons for drop-out and missing data will be recorded and will be reported in all reports and publications (**MD-2, MD-3, MD-5**).

**Plan for analysis of COVID-19 Pandemic impact:** We propose to add the following steps to the data analysis in order to take the pandemic into account: 1) Analyze the patterns and

causes of refusal to participation in the study before and during the pandemic to determine if the populations in the two periods are coming from the same base population; 2) Analyze the patterns of missing data, comparing them between before and during the pandemic to determine whether we need to additionally add an indicator of the time of data collection (before or during pandemic) as another factor in the generation of the imputed outcome data; 3) analyze the primary and secondary outcomes in an intention-to-treat manner as proposed in the protocol. We will follow with another data analysis that will add in the model time of data collection (pre/post pandemic) and its interaction with intervention type as possible explanatory factors to determine the potential impact of change in timing of enrollment or unaccounted for changes in the intervention.

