#### **Analysis of heterogeneity of treatment effects (HT-1, HT-3, HT-4)**

We will explore the differential effects of the intervention on patient subgroups defined by factors known or hypothesized to have associations with poorer TBI outcome: facility vs. community discharge, minority race/ ethnicity, older age, male gender, lack of or lower degree of caregiver

involvement, greater severity of TBI, presence of pre-injury psychosocial limitations (e.g., unemployment, substance abuse) and medical or psychiatric comorbidity, as well as study site, resource variability and insurance type. These factors will be entered in a single linear regression model in addition to the intervention group, using PART-O-17 as the response variable. Before constructing the model, we will assess whether the explanatory variables are correlated to each other. When two or more variables are deemed highly correlated, to avoid problems with collinearity, we will construct the model with the variable that provides the best model (from fit and diagnostic tests). From previous research, we hypothesize that severity of TBI and presence of pre-injury psychosocial limitations will interact with the intervention group, and those interactions will be included in the model. With our expected sample size we anticipate being able to address these questions.

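### Whether missing Aim 1 outcomes are imputed depends on a check the data cannot settle, and the sensitivity analysis drops any covariate with a missing value, including a moderator under test

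*Combined protocol and SAP*

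**What the plan says.** All the rules are in the section Data Analysis Plan Specific to Each Aim, under the general approach.

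- **Condition for imputing.** "When missing values are present we will check the missing mechanism", "and if it allows for imputation, we will do so according to the appropriate methods for a continuous variable". Multiple imputation is named, but there is no test, no criterion, no list of imputation variables, and no statement of what happens if the condition fails.
- **Sensitivity analysis.** For outcomes it is "the most conservative approach of removing the data from individuals with missing outcome values from the analysis". For covariates the rule continues: "or if it a missing value in a covariate, removing the covariate from the model". There is no threshold for how much must be missing and no exemption for moderators.
- **Reporting.** "The results of the analysis with imputed data and complete data will be compared to assess whether they differ and both results will be reported".
- **Longitudinal aims.** The mixed models are described as robust to gaps at single visits. That statement does not cover Aim 1, which is an unadjusted two-sided t-test at 6 months (and again at 12) for each primary outcome.
- **Heterogeneity.** The section Heterogeneity of Treatment Effects puts all factors in one regression on PART-O-17: "Interactions between each factor and the intervention group will be entered in the model and test of interaction will be the test of heterogeneity". The later section Analysis of heterogeneity of treatment effects adds that "we hypothesize that severity of TBI and presence of pre-injury psychosocial limitations will interact with the intervention group".

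**The concern.** The condition asks for something the data cannot supply. Observed data can contradict missing completely at random (MCAR). They carry no information on whether, given what was observed, the unseen scores differ from the seen ones. With no stated criterion, the analyst decides whether imputation is permitted once the results are within reach. If the answer is no, only the complete-case result remains for both primary outcomes. The plan calls that analysis the most conservative. This is not true in general, because its bias can go in either direction.

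The covariate rule has a different defect. A sensitivity analysis should ask the same question under another assumption about the missing data. Removing a moderator removes the interaction that is the test of heterogeneity, so that test has no sensitivity version. In the Aim 2 and Aim 3 models that adjust for covariates, dropping one changes the model as well as the data. A difference between the two results then cannot be attributed to missingness.

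**Working it through.** **1. The plan's own figure.** The recruitment table gives 900 patients and 80% retention. 900 × 0.20 = 180 lost and 900 × 0.80 = 720 retained. Both match the documents (180 in that table, 720 in the milestone schedule).

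**2. Detectable effect with 720 analysed** (two-sided 5%, 80% power, 360 per arm): (1.960 + 0.842) × √(2/360) = 0.209 SD. With the plan's SD of 0.75 this is 0.157 PART-O points.

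**3. Can the mechanism be checked?** Illustration with 100,000 simulated patients (all values assumed): covariate x standard normal, log-odds of response 1.5 + 0.5x, outcome 1.6 + 0.35x plus error of SD 0.6, and a shift δ added for non-responders only. About 19.3% are missing.

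| δ | Observed mean | Observed SD | Full-population mean |
|---|---|---|---|
| 0 (MAR) | 1.628 | 0.689 | 1.596 |
| −0.3 (MNAR) | 1.628 | 0.689 | 1.538 |
| −0.6 (MNAR) | 1.628 | 0.689 | 1.480 |

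The observed data are identical in the three rows, so no check on them can choose between rows.

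**4. Complete-case bias when missingness depends on the 3-month score.** Let log-odds(missing) = a + b × (3-month score in SD), with a set to give the required missing fraction. Bias in the arm difference = ρ × the gap between arms in the mean 3-month score of those observed, where ρ is the 3-to-6-month correlation. Assumed: 15% missing in one arm and 25% in the other.

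| b | Observed mean, 15% missing | Observed mean, 25% missing | Gap | Bias, ρ = 0.5 | Bias, ρ = 0.7 |
|---|---|---|---|---|---|
| −0.3 | 0.0445 | 0.0738 | 0.0293 | 0.015 | 0.020 |
| −0.5 | 0.0726 | 0.1195 | 0.0469 | 0.023 | 0.033 |
| −1.0 | 0.1326 | 0.2132 | 0.0806 | 0.040 | 0.056 |

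The range is 0.015 to 0.056 SD: 0.015/0.209 = 7% to 0.056/0.209 = 27% of the detectable effect. In PART-O points it is 0.75 × 0.015 = 0.011 to 0.75 × 0.056 = 0.042. The bias favours the arm with more missing outcomes. With the same missing fraction and the same mechanism in both arms, the gap is zero and so is the bias.

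**5. What imputation under MAR leaves open.** With 20% missing per arm, if RTP non-responders score 0.1, 0.3 or 0.6 points below what MAR predicts and RDP non-responders do not, the arm difference moves by 0.20 × δ = −0.02, −0.06 or −0.12 points. The 0.6 is the plan's minimal detectable difference; the rest is assumed.

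**6. The covariate rule.** The chance that a factor has at least one missing value among 900 patients is 1 − (1 − m)^900: 36% at m = 0.05%, 59% at 0.1%, 98.9% at 0.5%. The documents give no missingness rates for moderators, so m is assumed. Of the 11 listed factors, about five (site, discharge destination, age, sex, race) should be nearly complete. For the other six at m = 0.1%, assumed independent, the chance that none is removed is 0.999^(6 × 900) = 0.0045, and on average 6 × 0.594 = 3.6 are removed.

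**The case against.** **Both results are reported.** This is the strongest defence, and it stands when imputation is done: readers would see both estimates. It does not cover the case where imputation is judged not allowed, and the plan does not say which result governs if they differ.

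**Imputation is the working plan.** The COVID-19 paragraph speaks of generating imputed outcome data as if this were settled, and reasons for missingness are recorded. Both points are fair. They make imputation likely without making it a rule, and recorded reasons do not turn MNAR into MAR.

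**The condition does not run backwards.** A reader might infer that the plan tests for MCAR and withholds imputation if the test rejects, which is when imputation is most needed. The text names no such test and attaches no such consequence. It reads at least as naturally as imputing under MCAR or MAR.

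**The covariate rule is confined to a sensitivity analysis.** Correct. A reader might infer that the plan deletes moderators from the main heterogeneity model or affects the primary comparison. It does neither, and the heterogeneity work is largely exploratory. Nor do the documents support saying that most moderators would be lost. Site and destination are randomization strata, and age, sex and race are abstracted from the records of all screened patients.

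**The bias is small and rests on assumptions.** Also correct. The documents plan one retention figure and give no split by arm, and 0.056 SD is only about 11% of the 0.53 SD effect in the power section (0.056/0.533). Unequal loss is still plausible: patients enrolled by proxy who prove unable to take part are withdrawn at one month in RTP but at three months in RDP, and the retention section expects more contact to help retention, while only RTP adds about 12 contacts.

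**Conclusion.** The point holds on both parts, within limits.

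The handling of about 180 expected missing outcomes in the Aim 1 analysis depends on a condition that observed data cannot decide. No criterion is stated, and if the condition fails only the complete-case analysis remains. This needs no assumed numbers; it follows from the text and from step 3. The likely harm is modest: 0.015 to 0.056 SD under the assumed 15%/25% split, slopes and correlations, and about zero if missingness is the same in both arms. QoLIBRI is more exposed than PART-O-17, because proxies do not complete it and its gaps are therefore tied to impairment.

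The covariate rule, read as written, removes an incompletely recorded moderator and its interaction from the sensitivity version of the heterogeneity model, and it confounds the imputed-versus-complete comparison in the adjusted Aim 2 and Aim 3 models. TBI severity and pre-injury psychosocial limitations, the two hypothesized moderators, are not protected. How many factors would go cannot be determined from the documents.

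**What to change.** 1. Delete the condition. Make multiple imputation under MAR, done by arm and using baseline variables and the scores from other visits, the main handling for both primary outcomes in Aim 1. Keep complete-case as a sensitivity analysis and stop calling it the most conservative.
2. Add a delta-adjusted (tipping-point) analysis by arm. Imputation under MAR does not by itself answer the MNAR question.
3. State how deaths and QoLIBRI scores of proxy-respondent patients are treated. Neither should be imputed by default: death is a listed reason for non-completion, and the proxy QoLIBRI is missing by design.
4. Replace covariate removal with imputation of missing covariates within the multiple imputation, including arm-by-moderator terms and methods for categorical variables (the present wording covers only a continuous one). No covariate is dropped for missingness.

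The cost is plan wording and a little more analysis work; no new data are needed. The milestone schedule ends follow-up on 31 October 2022 and completes analyses by 15 July 2023, so the change should be dated and fixed before any comparison by arm.

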    - ii. If No: Staff will deem the patient ineligible due to inability to complete study procedures due to cognitive/verbal limitations AND not having a proxy to assist with study procedures.

\*If the proxy individual is not enrolled as a caregiver participant in the study, the TCM would only engage the proxy individual in resource facilitation and the needs assessment as it specifically pertains to the patient participant. The TCM will not conduct a caregiver needs assessment with the proxy or provide resources that pertain specifically to the proxy individual as they are not enrolled as a caregiver. If the TCM infers that the proxy individual would like to participate in the needs assessments/resource facilitation as it pertains to them (e.g., as the caregiver), the TCM would remind the proxy individual in a non-coercive manner of the opportunity to participate as a caregiver participant. This would require the completion of the informed consent process with the proxy individual as per study protocol.

\*\*In this scenario, the proxy individual would not complete the QOLIBRI as part of the post-discharge questionnaire. In addition, the individual would not complete the following items on the Form II: SWLS, GEN, GNHLTH, PHQ, GAD

\*\*\*Staff will withdraw the patient participant following randomization if the participant is deemed unable to participate due to limitations within the following timeframes:

1. The TCM will withdraw the patient participant one month following discharge if randomized to RTP arm of the study;
2. Blinded staff will withdraw the patient participant three months following discharge if randomized to RDP arm of the study;

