Estimated lost to follow up/attrition of patients	Historically, the procedures for participant recruitment and retention used in TBIMS sites has a 90% retention benchmark, and <10% missing data. Given this is a more complex trial requiring increased engagement over time, we anticipate having a more difficult time with retaining participants and therefore are planning for an 80% retention mark.	180
Estimated lost to follow up/attrition of caregivers		110
Estimated monthly enrollment of patients		23-24
Estimated monthly enrollment of caregivers		13-14

Our 80% estimate is based on both our benchmark expectation for enrollment into the TBIMS as well as recruitment rates from the prior intervention studies completed by our team detailed below that have enrolled from the TBIMS population.

Given the broad inclusion criteria and flexibility and provision of treatment that is standard care or higher in both intervention groups, we anticipate meeting our planned recruitment rate.

- (1) The six TBIMS centers in this grant have an average enrollment of 81.35% for TBIMS.
- (2) Bell et al. had a 95% enrollment rate into a single-site study with similar study population and methodology.
- (3) In a multi-site study among 3 TBIMS sites with similar study population and methodology, we had a 90% enrollment rate among those who were eligible.

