### **Power Analysis**

As can be seen in the Recruitment/Enrollment table above (p. 26), we expect to enroll a minimum of 300 individuals per year for 3 years (total N = 900). We based our power calculation on the PART-O-17, the primary outcome for which we have the most relevant data in TBI. Unpublished data from a sample discharged from inpatient TBI rehabilitation showed a PART-O-17 Total (which can range from 0 to 5) average score of 1.51 (SD=0.65) at 3-months follow-up and 1.66 (0.72) at 9-months follow-up (publication in preparation). Minimal detectable differences (MDD) were 0.57 and 0.63 at 3 and 9 months, respectively. Using these results, we calculated the power of finding a difference of 0.60 (average of the two MDDs) between the two groups under various assumptions as follows:

Test: t-test for independent samples, two-tailed, allocation ratio=1

[figure not shown]
Significance level=0.05

Common standard deviations: 0.75 (higher than the observed in previous studies to be conservative)

Mean PART-O scores (Intervention mean minus control mean): The minimal detectable difference of the instrument is 0.6. To be more conservative, we started the difference between the two means at 0.4. Assuming SD=0.75 (in the higher side of previous studies) the calculated effect size based on this mean and SD is 0.5333. Therefore, we used values of 0.5 to 0.8 by increments of 0.05 for the effect sizes.

[figure not shown]
Sample sizes: from 500 to 900 individuals (by 100)

The graph shows that even with an effect size of 0.5 (corresponding to a difference of 0.4 points between the two groups and under an SD larger than those observed in prior studies), we have practically 100% power to detect the difference between the two groups with sample sizes of 500 and above (we expect to have 900).

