### **Data Analysis Plan Specific to Each Aim (IR-3, IR-5)**

**General approach:** The expected sample size is very large and we anticipate 100% power to find a difference in PART-O-17, if a difference exists. In addition, the sample size will allow us adequate power to examine our other aims and heterogeneity of treatment effects. We will use a significance level of 0.05 for all the analyses we will perform. Given the large sample size and the extremely high power for the primary outcome, we will not adjust the significance level for multiple comparisons for all the other tests, since it is highly likely that the p-values for those tests will be small. As it is well known and now stated in a publication by the American Statistical Association, the p-value should not be the single deciding measure of the significance of a result. Therefore, we will interpret the results of all non-primary outcomes with caution and will examine effect sizes as well as explicitly report the secondary outcomes status when presenting the results. We will obtain input from our stakeholders regarding the meaningfulness and importance of the effects.

The analysis plan will conform to the intent-to-treat principle: all randomized cases will be included based on their assigned treatment group regardless of actual intervention received. Missing values will be prevented and minimized by implementing the following steps in the manual of operations: 1) Prompt data entry to allow timely detection of any missing data, 2) Procedures for monitoring and tracking data completeness will be in the manual of operations, 3) When missing data are identified, research staff will contact the participant to collect them (if not time-contingent or outside the specified time range for collection). At the end of the study, participants not assessed at the end of intervention will be considered as having missing outcome values.

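### The only sensitivity analysis for missing outcomes is complete-case analysis; it is mislabelled as conservative, nothing tests departure from missing at random, and death has no analysis rule

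*Combined protocol and SAP*

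**What the plan says.** The general approach in the Data Analysis Plan Specific to Each Aim states that "participants not assessed at the end of intervention will be considered as having missing outcome values". The missing-mechanism is then checked and, if it permits, missing values are multiply imputed. The sensitivity analysis repeats the work "using the most conservative approach of removing the data from individuals with missing outcome values from the analysis". The imputed and complete-case results are compared and both are reported.

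The COVID-19 paragraph may add a period indicator to the imputation model and adds a period-by-arm analysis. The longitudinal aims use mixed models. The primary comparison under Aim 1 is an unadjusted two-sample t-test at 6 months.

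On the amount of loss, Table 1 (Recruitment/Enrollment Assessment Timeline) says "we anticipate having a more difficult time with retaining participants and therefore are planning for an 80% retention mark", which it counts as 180 patients.

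Under Recruitment, the text on patients unable to consent says that a proxy does not complete the QoLIBRI. For one subgroup it sets withdrawal for inability to participate at one month in RTP, by the care manager. For the other arm it says: "Blinded staff will withdraw the patient participant three months following discharge if randomized to RDP arm of the study".

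Death appears in Questionnaire Scheduling and Timing and in Participant Retention as one reason among others for an uncompleted questionnaire, and in the safety section as a serious adverse event outcome. No analysis rule is attached to it.

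**The concern.** A sensitivity analysis for missing data should ask what happens if the main assumption fails. Multiple imputation, as planned, assumes data missing at random (MAR): given what was observed, missing patients resemble observed ones. Complete-case analysis with an unadjusted t-test does not relax that assumption. It tightens it, because observed patients must then represent all patients in their arm without help from earlier scores. The COVID-19 indicator and the mixed models also stay within MAR.

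The mechanism check does not close the gap, because observed data cannot separate MAR from missing not at random (MNAR). If the check rules imputation out, complete-case becomes the main analysis and no sensitivity analysis is left.

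The protocol gives its own reasons to doubt MAR: 20% expected loss, QoLIBRI scores missing by design where a proxy answers, and a withdrawal rule tied to impairment whose timing and assessor differ by arm. At stake is a robustness statement about the primary result that could read as reassuring without having tested the relevant threat.

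**Working it through.** **Inputs.**
- Power Analysis: N = 900; "Test: t-test for independent samples, two-tailed, allocation ratio=1"; "Significance level=0.05"; SD 0.75 for PART-O-17; planned difference 0.40 points.
- Table 1: 80% retention.
- Power Analysis Revisited: smallest effect size considered, 0.3.
- Assumptions of this check, not in the documents: the gap between missing patients and their imputed values, and the 3- to 6-month correlation.

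**1. The plan's own figures.** 900 × (1 − 0.80) = 180 lost, leaving 720. Appendix 1 also counts 720 as all 6-month follow-ups. Planned effect size 0.40/0.75 = 0.533. Power at N = 500 and effect size 0.5 is 0.9999, which agrees with the plan's claim of practically full power.

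**2. What each analysis gets wrong.** With missing fraction m in one arm:
- complete-case bias = m × (mean of observed − true mean of missing);
- imputation bias = m × (mean imputed for missing − true mean of missing).

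The two are equal only when the imputed mean equals the observed mean, that is, when earlier scores do not predict who drops out.

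**3. Size for the imputed analysis.** Missing RTP patients worse than imputed by a gap g; missing RDP patients not:
- g = 0.25 SD: 0.20 × 0.25 = 0.05 SD
- g = 0.5 SD: 0.20 × 0.5 = 0.10 SD
- g = 1.0 SD: 0.20 × 1.0 = 0.20 SD

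Detectable effect at 360 per arm with 80% power: (1.96 + 0.84) × √(2/360) = 0.209 SD. So 0.10 SD is about 48% of the detectable effect (0.10/0.209) and about 19% of the planned one (0.10/0.533).

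**4. Simulation.** N = 900, about 20% missing per arm, SD 0.75, true difference 0, 400 runs, 10 imputations within arm from the 3-month score. In RTP, P(missing) = 1/(1 + exp(1.75 + 1.2z)), where z is the standardised score driving dropout. In RDP, 20% are missing at random. Bias is in PART-O-17 points; positive favours RTP; simulation error is about 0.003.

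| Dropout in RTP depends on | Correlation | Complete-case | Imputation |
|---|---|---|---|
| 6-month score (MNAR) | 0.5 | +0.149 | +0.116 |
| 6-month score (MNAR) | 0.7 | +0.148 | +0.082 |
| 6-month score (MNAR) | 0.8 | +0.144 | +0.056 |
| 3-month score (MAR) | 0.5 | +0.073 | −0.001 |
| 3-month score (MAR) | 0.7 | +0.101 | −0.002 |
| 3-month score (MAR) | 0.8 | +0.116 | −0.001 |

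With dropout completely at random, or the same MNAR mechanism in both arms, both biases are about 0. Exchanging the arms reverses the signs. For scale, the standard error at 720 patients is 0.75 × √(2/360) = 0.0559, so the smallest significant difference is 1.96 × 0.0559 = 0.11 points.

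**5. Tipping point.** Shift in missing RTP patients at which significance is lost = (observed difference − 1.96 × SE)/m, taking the SE as that of the observed patients.

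| Observed difference | 10% missing | 20% missing | 30% missing |
|---|---|---|---|
| 0.40 (planned) | 2.97 points | 1.45 points (1.94 SD) | 0.94 points |
| 0.225 (0.3 SD) | 1.22 points | 0.58 points (0.77 SD) | 0.36 points |
| 0.15 (0.2 SD) | 0.47 points | 0.20 points (0.27 SD) | 0.11 points |

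Example: (0.40 − 0.1096)/0.20 = 1.45 points; 1.45/0.75 = 1.94 SD.

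**The case against.** The other side has good points, and most of them limit the claim.

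- **A reader might infer that complete-case simply repeats the imputation bias, so the comparison is worthless.** That is too strong. Under MAR in RTP only, complete-case is biased and imputation is not. Under MNAR in RTP only, both lean the same way by different amounts. Disagreement is therefore informative, and the plan commits to reporting it. What stands is that agreement cannot exclude MNAR.
- **A reader might infer that deaths will be imputed as if the patients were alive.** The plan never says so, and imputation depends on the mechanism check. What stands is that the definition of a missing outcome makes no exception for death, so a death before 6 months is open to imputation. Death is recorded as a reason for no follow-up, and reasons for drop-out are to be reported.
- **A reader might infer that impaired patients in general are withdrawn at different times by arm.** The rule covers only patients enrolled by proxy consent, with no assisting person, whom clinical staff thought more likely than not to be able to take part within a month. Both time points precede 6 months. The section on Withdrawal/Discontinuation says staff stop data collection in only two circumstances, neither of them inability, while its Discontinuation subsection says withdrawn participants do no further procedures. Whether these patients lose their 6-month outcome is therefore unresolved.
- **PART-O-17 is partly protected.** It accepts proxy report, and a significant other can be mailed the questionnaire. The QoLIBRI is not completed by proxies.
- **Loss may be smaller.** Data Management still anticipates the low missing rates of the parent cohort. But Table 1 plans for 80% retention, and the 10% column above shows the more favourable case.
- **At the planned effect the result would be robust.** This stands: 1.94 SD is a very large shift.

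**Conclusion.** The concern holds in limited form. Complete-case analysis is the only planned sensitivity analysis for missing outcomes. Its label is wrong as a statement about bias, and no planned analysis tests departure from MAR. In both RTP-only dropout scenarios it favoured RTP more than the analysis it is meant to check.

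The size rests on assumed gaps, because the documents give none. The 0.10 SD in the imputed analysis assumes 20% missing and a 0.5 SD gap in RTP only. The complete-case bias should not be given the same figure unless earlier scores do not predict dropout. An observed 0.3 SD effect would lose significance at a shift of about 0.77 SD; the planned 0.40-point effect would need about 1.94 SD. The gap therefore matters mainly if the effect is smaller than planned, and the documents do not support reading it as a threat to a result of the planned size.

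For death, the finding is only that no rule exists. Without a death rate its effect cannot be sized.

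**What to change.** In the missing-data text of the Data Analysis Plan:

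1. Delete the description of complete-case analysis as most conservative, and keep it as a supplementary analysis.
2. Make delta-adjusted multiple imputation the main sensitivity analysis for 6-month PART-O-17 and QoLIBRI. Vary the shifts separately by arm, extend them until significance is lost and report the tipping point. A grid capped at −1 SD would stop short of the 1.94 SD tipping point at the planned effect. Run this whatever the mechanism check shows.
3. State that outcomes after death are not imputed as ordinary missing values, state how deaths enter the intent-to-treat comparison, and report deaths by arm.
4. Reconcile the subgroup withdrawal rule under Recruitment with the Withdrawal/Discontinuation section, so that it is clear whether 6-month outcomes are still sought for these patients.

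No new data are needed, since reasons for missingness are already recorded. The cost is SAP wording, a little more analysis, and possibly a less favourable robustness statement.
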